3 STATISTICAL METHODS

3.1 Statistical analysis strategy

The statistical analyses will be performed in accordance with the ICH E9 guideline and will be based on the pooled data from the individual study sites, unless otherwise stated.

Medpace will perform the statistical analysis of the efficacy, safety, and antibodies data.

Overall, the analysis strategy is to evaluate safety and efficacy of Dysport compared to Placebo after single administration (DB period), and to evaluate efficacy and safety over repeated Dysport treatments, using analyses by Active Treatment Cycle.

Listings will be presented by subject for DB and OL periods together while the tables associated with the DB period will be separated from the tables assessing repeat treatment with Dysport.

Only descriptive statistics of Stage 1 data will be provided.

Double-Blind Period (Stage 1 Cycle 1) Analyses

For the analysis of the DB period, tables will be displayed using the following treatment group (DB treatment group) labels, in the following order:

- Placebo: placebo groups from all cohorts will be pooled, including for mVPAQ pain, mVPAQ life interference and mFSFI pain domain of cohort 1 despite the change in recall period and time of assessments (see protocol version 3.0).
- Dysport
 - Groups by dose (Dysport 100U, 300U, 400U, 500U, etc.)
 - All Dysport

[figure not shown]
Note: Cohort 1 (100U), 2 (300U), 3 (400U) and 5 (500U) included PVD2 subjects only. Cohort 4 (400U) and 6 (500U) included PVD1 subjects only.

Repeat treatment: Active Treatment Analyses

To assess efficacy and safety data over repeat treatments, data will be analysed using the Active Treatment Cycle approach as described in [Figure 1](#) below. These analyses will be performed on the Active Treatment population:

- for subjects treated with Dysport in the DB period, the first cycle in the DB period will be the first Active Treatment Cycle.
- for subjects treated with placebo in the DB period, the first cycle in the OL period will be the first Active Treatment Cycle.

[Figure 1](#) Active Treatment Cycle Analysis

Three types of summary tables will be produced:

- Summary by number of active treatment cycles: these tables will present the long-term efficacy and safety data with all doses combined, and will display subjects with at least 1 (2, 3 and 4) active treatment cycles.
- Summary by dose received at each active treatment cycle: to evaluate the safety of each dose at a given cycle.
- Summary over the whole trial (restricted to Week 6 and 12 from DB and from first OL period) by the randomised treatment group (DB treatment group) may be provided for some efficacy analyses.

The type of summary table(s) used for each endpoint are described in sections [3.8](#) and [3.9](#).

Descriptive Statistics

All raw and derived variables will be listed and described using summary statistics. For categorical variables, summary statistics will be displayed by frequency counts and percentages by category. The missing category will be presented if there is at least one missing data in a treatment group. Except otherwise specified, subjects with missing data will be included in the calculation of percentages. For quantitative

variables, summary statistics will be displayed using descriptive statistics by number of observations, mean, standard deviation (SD), median, minimum and maximum.

3.1.1 ***Multiplicity***

No multiple testing will be performed.

3.1.2 ***Significance testing and estimation***

As this is a descriptive safety study, no formal statistical testing will be carried out based on Stage 1 data.

3.1.3 ***Withdrawal visit and end of study visit***

Subjects who have withdrawn early from the study have their last assessment (during early withdrawn visit) mapped as visit 90 in the Study Data Tabulation Model (SDTM). By convention, for these subjects, the visit number will be reassigned to the next empty visit number for analysis (i.e. if a subject has only Visit 1, 2, 3 and 90 entered in the database, the visit number 90 will be reassigned to visit number 4). End of study visits will be described separately as “End of Study (Cycle X)”.

3.2 **Subject disposition and population**

The following disposition summaries and listings will be provided:

- Number and percentages of randomized subjects per country and site by DB treatment group.
- Number and percentages of subjects screened, screen failed and reason for screen failure, randomized, treated, completed, withdrawn and reason for withdrawal by DB treatment group.
- Listing of date of visit.
- Listing of screen failure subjects.
- Listing of withdrawn subjects (on the randomised population).

The following population summaries and listings will be provided:

- Number and percentage of subjects in each analysis population with reasons for exclusion from each population, for the DB treatment group and overall, based on all randomized subjects.
- Listing of randomization details.
- Listing of subjects who don't meet eligibility criteria (violated inclusion criteria, fulfilled exclusion criteria).
- Listing of subjects including flag for each analysis population and reason for exclusion from each population.

3.3 **Protocol Deviations**

A list of major protocol deviations and any action taken have been defined in the Protocol Deviation Plan. Subjects with major protocol deviations will be determined before database lock and unblinding of the study. A final review will be done during the blind data review and documented in the protocol deviation listing. Confirmation of major deviations related to treatment and dose will be done after unblinding.

Number and percentage of subjects with major protocol deviations will be summarized by deviation category for all randomized subjects. A Listing of major

protocol deviations will also be provided. COVID-19 related protocol deviations will be flagged.

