The psychometric properties of the dilator-induced pain Numeric Rating Scale (NRS), dilator size 6 insertion pain NRS, pain on intercourse NRS, mVPAQ, and modified Female Sexual Function Index (mFSFI) were to be evaluated using data collected from all subjects randomized in Stage 1 and Stage 2. The planned analyses of these data are described in the Psychometric Analysis Plan of validation study D-FR-52120-252. However, these analyses were cancelled following the decision to prematurely terminate the study.

1.3.5 ***Data review Committee and planned Analyses***

Data Review Committee

A DRC has been established to make recommendations for dose escalation and dose de-escalation or study termination decisions in Stage 1. It was planned that (a) if no subject reports a clinically significant AE (defined in the protocol section 3.1.1.1) in a cohort, the DRC will meet once all PVD2 and PVD1 evaluable subjects of a dose level have reached Week 6 to review the unblinded efficacy and safety data and decide the dose for the next cohort or proceed to Stage 2; (b) If any subject reports a clinically significant AE, then further enrolment into the cohort as well as retreatment in open label cycles at the current dose will be suspended and an ad hoc DRC meeting will be scheduled to review the data and make a recommendation with regards to further conduct of the cohort and of Stage 1.

Details related to DRC membership, responsibilities, procedures, role and remit are described in the DRC charter.

Early Study Termination Decision

Following the DRC meeting organized to review safety and efficacy data of cohorts 1 to 6 on the 16 OCT 2020, the DRC sent the following recommendation:

"No safety concerns noted in review of all available data. Efficacy cannot be assessed due to the small sample size of cohorts. The DRC would recommend that Stage 1 is not used to make an efficacy assessment, therefore there is no justification to increase the dose, nor to move to Stage 2."

Ipsen subsequently decided to close the study early and to run the final analysis based on available Stage 1 data. Subjects in the study are followed until 12 weeks after the last dose as described in the protocol section 3.9.

Final Analysis

The final analysis will be carried out once all subjects from cohorts 1 to 6 have completed end of study evaluation, after the database lock. All unblinded safety and efficacy data available at the time of the database lock will be analysed.

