No control of the overall type I error rate is planned as only exploratory descriptive statistics are planned.

2 **SUBJECT POPULATIONS (ANALYSIS SETS)**

Screened population

The screened population is all subjects screened (i.e. who signed the informed consent).

Randomized population

Randomized population is all subjects randomized (i.e. who were randomly allocated to a treatment group).

modified Intent-To-Treat population

The modified Intent-to-Treat (mITT) population is all randomized subjects who received at least one IMP administration and had data for the vaginal dilator induced pain as reported on an 11-point NRS [using the Dilator Maximum Tested Size (DMTS) reported at Baseline] at Baseline and Cycle 1-Week 6 visit (i.e. at least one pain score for one dilator size, which enables an imputed pain score of 10 at DMTS if needed).

The mITT population will be analyzed using subjects as randomized.

Active Treatment Population

The Active Treatment Population is all randomized subjects who received at least one dose of Dysport (including only partial administration) during the DB and/or OL period.

Safety

The safety population is all randomized subjects who received at least one dose of IMP administration (including only partial administration).

The safety population will be analyzed using subjects as treated (i.e. according to actual treatment received).

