3.8 Efficacy analysis

The efficacy endpoints will be summarized using the analysis strategy in Section 3.1. Descriptive statistics will be provided for:

- the DB period, by DB treatment group for the mITT population.
- the Active Treatment Cycle, on the Active Treatment population: by number of active treatment cycles (all doses combined and/or by dose). The mITT population will be the primary population for analysis of efficacy data. Week 6 and Week 12 will be the timepoints of primary interest.

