3.8.2 Secondary efficacy analyses

Vestibular pain using a vaginal dilator

A set of 8 vaginal dilators of increasing diameter (#1 being the smallest and #8 being the largest) will be used to provoke pain to allow assessment of the vestibular pain intensity in each subject. Subjects will be required to rate the pain for each dilator size on an 11-point NRS at each visit. Pain score will be entered by the investigator (or delegated site staff) in the eCRF.

Based on the subjective pain threshold, the largest sized dilator that the subject accepts to test, will be defined as the Dilator Maximum Tested Size (DMTS) that will be established at the Baseline Visit. The dilator test will be used to assess the change from Baseline in the vaginal dilator induced pain as reported on an NRS (using the DMTS reported at baseline) as well as the dilator size that provokes maximum pain. If a dilator size is not tested due to pain intensity, the pain will be scored at 10. If the test is not done due to other reasons, then the pain score will be considered as missing. Endpoints and corresponding analyses are described in [Table 1](#).

Table 1 Dilator Induced Pain - Endpoints and Corresponding Analyses

Endpoint	Analyses
Mean change from Baseline to each post-treatment visit in the vaginal dilator induced pain as reported on the 11-point NRS[1]	
Convention:
 
According to the mITT Population definition, there will be no missing data for Week 6. For Week 12, the missing values will be kept as missing.
 
- descriptive statistics: actual values and change from baseline values will be presented at all timepoints (over the double-blind and open-label periods). A plot of mean changes over time from baseline in pain scores will be provided by treatment group for DB period.
 
Active Treatment Cycle:
 
 - A summary by number of active treatment cycles. - A plot of mean changes over time from baseline in pain scores will be provided by randomized treatment group for Week 6 and Week 12 over both of the DB and first OL period.
Proportion of subjects who reported at least a 50% decrease in vaginal dilator induced pain as reported on the 11-point NRS[1] at each post-treatment	
Convention:
 
According to the mITT Population definition, there will be no missing data for Week 6. For Week 12, the missing values will be kept as missing.
 
- descriptive statistics will be presented at all timepoints.

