For events within the i^{th} cycle, the treatment cycle day = date of event - (date of (i)th injection) +1.

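### SAP 3.1.3 places an early-withdrawal assessment at the next empty visit whatever its day, so off-window values can be tabulated as Week 12 and, in some tables, as Week 6

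*SAP*

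**What the plan says.** SAP 3.1.3 deals with subjects who leave early. Their last assessment is stored as Visit 90 and, by convention, "the visit number will be reassigned to the next empty visit number for analysis". The SAP's example is a subject with Visits 1, 2, 3 and 90, whose Visit 90 becomes Visit 4. End-of-study visits are handled differently: they keep their own label with the cycle number. Nothing in 3.1.3 refers to the day of the withdrawal visit, and SAP 3.8, 3.10, 3.11 and 3.12 contain no analysis window.

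Four other SAP statements matter here:

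- SAP 3.8: "Week 6 and Week 12 will be the timepoints of primary interest".
- SAP section 2: the mITT needs dilator pain data "at Baseline and Cycle 1-Week 6 visit", and nothing at Week 12.
- SAP 3.8.2, Table 1, on dilator pain: "For Week 12, the missing values will be kept as missing".
- SAP 3.1, Descriptive Statistics: unless specified otherwise, "subjects with missing data will be included in the calculation of percentages".

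In protocol Table 2, Visit 3 is the Week 2 telephone contact, Visit 4 is Week 6 and Visit 5 is Week 12. Under protocol 5.2.4 the withdrawal visit includes the dilator test, haematology and biochemistry, so there are efficacy and laboratory values to relabel.

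**The concern.** A visit label should say when a value was measured. Under this rule it says only which slot was free. A subject can be in the mITT on the strength of her Week 6 test, withdraw some weeks before Week 12 is due, and still appear in the Week 12 row as if seen on time. If she skipped Week 12 and left later, the error runs the other way.

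Week 12 is one of the two efficacy timepoints that the SAP singles out, and the dose groups are small, so a single record is visible in a mean or a responder percentage. Laboratory change is also summarised by timepoint (SAP 3.9.3), and Week 12 is a scheduled laboratory visit (protocol 5.2.2.4). The same relabelling therefore reaches safety tables.

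**Working it through.** **1. The SAP's own example.** Visits {1, 2, 3, 90} give Visit 4, Week 6. This holds whether the next empty number means the lowest unused number or the one after the last visit attended.

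**2. Windows (protocol 5.2.2.3 to 5.2.2.5).**
- Week 6: 43 ± 5 = Day 38-48
- Week 12: 85 to 85 + 14 = Day 85-99
- Week 18: 127 ± 14 = Day 113-141

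**3. Week 12, early withdrawal.** Visits {1, 2, 3, 4, 90} give Visit 5, Week 12, on either reading. The earliest case is Week 6 attended on Day 38 and withdrawal on Day 39: 85 − 39 = 46 days early. With Week 6 on Day 43, withdrawal on Day 44-84 is 41 to 1 days early.

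**4. Week 12, late withdrawal.** With the same visit set, a withdrawal in the Week 18 window is also labelled Week 12. That is 113 − 99 = 14 to 141 − 99 = 42 days after the Week 12 window closes.

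**5. Weight of one record at Week 12.** Planned sizes come from protocol 3.1.1 and SAP 1.3.2, for Cohorts 1 to 6. Because missing subjects stay in the denominator, filling one empty cell adds up to 1/n to a responder rate. If missing subjects were excluded, the rate would move from k/(n−1) to k/n or (k+1)/n, and the largest change is again 1/n. For a mean, a value that differs by d from the mean of the others shifts it by d/n. The documents give no d, so I assume 2 to 4 NRS points.

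| Group | n | 1/n, percentage points | Mean shift, d = 2 to 4 |
|---|---|---|---|
| 100 U | 8 | 12.5 | 0.25-0.50 |
| 300 U | 8 | 12.5 | 0.25-0.50 |
| 400 U | 8 + 6 = 14 | 7.1 | 0.14-0.29 |
| 500 U | 8 + 8 = 16 | 6.25 | 0.13-0.25 |
| Pooled placebo | 6 × 2 = 12 | 8.3 | 0.17-0.33 |
| All Dysport | 46 | 2.2 | 0.04-0.09 |

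The 100 U subjects (Cohort 1) followed protocol Version 2.0, whose Week 12 window is not shown. The 300 U group gives the same figures without that uncertainty.

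**6. Week 6.** A subject with Visits {1, 2, 3, 90} is labelled Week 6 whatever the day. If she is seen on Day 85-99, that is 85 − 48 = 37 to 99 − 48 = 51 days after the Week 6 window closes. The tables exposed are these:
- *Double-blind mITT efficacy tables:* only if mITT membership is judged after relabelling. The SAP does not give the order.
- *Active Treatment summaries:* in either order. SAP 3.1 says of the tables by number of cycles that "these tables will present the long-term efficacy and safety data with all doses combined", but SAP 3.8 also allows them by dose.
- *The Week 6 and Week 12 plot in SAP Table 1:* in either order. It is drawn by randomised group.
- *Laboratory summaries by timepoint on the Safety population:* in either order. No laboratory test is scheduled at Week 6, so a relabelled sample would create a Week 6 laboratory entry.

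With all doses combined (at least 46 subjects at planned sizes), one subject is about 2%. In a by-dose or by-group display she can be 1/8 = 12.5%, so 2% is not an upper bound.

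**7. Cases that do not matter or are unclear.** Visits {1, 2, 90} go to Visit 3, the telephone contact, and reach neither timepoint. Visits {1, 2, 4, 90} become Visit 5 or Visit 3 depending on how the next empty number is read.

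**The case against.** The convention is prespecified and has a worked example. It also keeps an observed value from a subject who would otherwise contribute nothing at that visit.

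A reader might infer that SAP 3.1.3 contradicts the statement in SAP Table 1 that missing Week 12 values stay missing. The documents do not support that. The two rules can be applied in sequence: visits are mapped first, and cells still empty are then left missing. The fault is the absence of a day condition.

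Many labels may also be right. After the early closure, SAP 1.3.5 has subjects followed to 12 weeks after the last dose, which for a Cycle 1 subject is about Day 85. Protocol 4.4 asks for the same, but it also accepts observation only up to the time of withdrawal, so the problem cases become fewer and are not excluded.

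The figures above are largely 1/n, and any value in a group of 8 carries that weight. The 46-day case is an extreme. Listings of visit dates and withdrawn subjects (SAP 3.2) let a reader trace each record, although they do not correct the table or the plot. All of this limits the size of the point but does not remove it.

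**Conclusion.** The point holds, with minor impact. Followed exactly, SAP 3.1.3 can place off-window dilator and laboratory values in Week 12 summaries as if they were on time. One record can move a by-dose responder rate by 6.25 to 12.5 percentage points at planned sizes, or pooled placebo by 8.3. These are maxima per record and not probabilities, because the number of Visit 90 records is not given. The mean shifts also rest on the assumed 2 to 4 point difference.

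A reader might infer that the double-blind Week 6 mITT results are certainly affected. That depends on an order of operations that the SAP leaves open. A reader might equally infer that Week 6 exposure is confined to pooled tables at about 2% per subject, and the by-dose summaries and the plot by randomised group rule that out.

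Nor do the documents support a claim that a conclusion of the trial is at risk. Stage 1 is descriptive with no testing, its primary objective is safety, and SAP 1.3.5 records the committee's view: "The DRC would recommend that Stage 1 is not used to make an efficacy assessment".

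**What to change.** Before database lock, replace the convention in SAP 3.1.3 with wording such as: *A Visit 90 assessment is assigned to a scheduled visit only if its treatment cycle day falls within that visit's protocol window and that visit is empty. Otherwise it is presented as Early Withdrawal (Cycle X).* This mirrors what is already done for end-of-study visits. The variable needed is already derived: SAP 3.11, item 8, starts from "the treatment cycle day = date of event", subtracts the cycle's injection date and adds 1. The Cycle 1 windows are those in step 2 of the working.

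Also:
- apply the rule to efficacy and laboratory tables alike;
- state in SAP section 2 that a Visit 90 assessment meets the mITT Week 6 requirement only if it is in window;
- reconcile the two open-label Week 12 windows (+14 days in protocol Table 3, ±14 days in protocol 5.2.3.4) before using the rule there;
- list the change in SAP section 5.

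The cost is SAP wording and a date-based mapping. A few Week 6 or Week 12 cells become missing. Those subjects stay in percentage denominators, so an observed responder moved out of the row then counts like a non-responder. A few subjects may leave the mITT. Withdrawals on Day 49-84 or Day 100-112 fall in no window and appear only under the early-withdrawal label. Scheduled visits attended off-window keep their nominal label, so the rule does not remove every mistimed value; the visit-date listing shows the rest.

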#### **5.2.4 End of Study Visit or Early Withdrawal Visit**

The procedures to be carried out at the EOS Visit or EWD Visit are identical.

The following procedures will be performed at the EOS, or EWD visit (the procedures already performed on the same day at the previous study visit do not need to be repeated):

- mFSFI (pain to be recorded 1 week prior to the visit and at the visit; other domains to be recorded only at the visit; only if the EOS/EWD visit occurs during the double-blind period)
- mVPAQ (pain and life interference to be recorded 1 week prior to the visit and at the visit; other subscales to be recorded only at the visit; only if the EOS/EWD visit occurs during the double-blind period)
- PHQ-9 only if the EOS/EWD visit occurs during the double-blind period
- SF-36 (only if the EOS/EWD visit occurs during the double-blind period)
- PGI-S (to be recorded 1 week prior to the visit and at the visit)
- PGI-C (to be recorded 1 week prior to the visit and at the visit)
- Relationship/partner status (to be recorded weekly from 2 weeks prior to the visit and at the visit)
- Intercourse details (to be recorded daily from 2 weeks prior to the visit)
- Dilator size 6 insertion details (to be recorded weekly from 2 weeks preceding the visit; assessment on the day of the visit should be avoided)

- Urine pregnancy test
- Urine test for illicit drugs
- Blood sampling (nonfasting) for haematology, biochemistry and putative antibodies
- Dilator test
- CGI
- Review of AEs
- New or changed concomitant medications/nondrug therapies.

If the COVID-19 pandemic prevents subjects from coming to the site, EOS visits should be postponed until onsite visits resume.

Subjects who attend the EOS Visit will be considered to have completed the study.

Subjects with ongoing AEs or clinically significant laboratory test abnormalities (as determined by the investigator) will be monitored as described in Section 8.1.5 and Section 8.1.2.4, respectively.

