#### *11.4.2 Subject Disposition and Withdrawals*

The numbers and percentages of subjects screened, randomised and included in the analysis populations will be tabulated. The reasons for subject exclusions from each of the populations will also be tabulated. In addition, the numbers of subjects who discontinued and completed at each of the study periods (double-blind treatment period and open-label period) will be tabulated. Primary reasons for discontinuation of study treatment will be tabulated.

The impact of COVID-19 pandemic on the trial will be assessed through the summary of data collected in relation to COVID-19, i.e. disposition of patients including the proportion of patients impacted and withdrawn due to COVID-19 pandemic and number of patients with visits impacted by COVID-19 with the corresponding reason. Exposure to treatment will also be described before and after the start of COVID-19 pandemic (i.e. before/after first patient randomised in Cohort 6).

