1.2 Study design

This is a Phase II multicentre, double-blind (DB), randomized, placebo-controlled, dose finding study to define the optimal doses of Dysport and evaluate its efficacy and safety compared to placebo in vulvodynia patients with PVD. Study treatment was injected at 5 needle insertion points at 10 injection sites in the vestibular area. The study consisted of a dose escalation stage (Stage 1) and a dose expansion stage (Stage 2). The purpose of the dose escalation was to determine the Dysport doses to be further investigated in Stage 2. Both Stage 1 and Stage 2 consisted of a DB period (treatment cycle 1; Dysport or placebo) followed by an open-label (OL) treatment period (treatment cycles 2 to 4; all subjects receive Dysport).

However, the study was terminated before Stage 2 begins (please refer to Section 1.3.5).

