3.9 Safety

For the DB period, summary tables by DB treatment group will be provided on the Safety population.

For the Active Treatment Cycle, summary tables by number of active treatment cycles will be provided on the Active Treatment population. Additionally, a summary table will be also provided by dose received at each active treatment cycle on the Active Treatment population.

The summary tables will follow the strategy specified in Section 3.1.

3.9.1 *Extent of exposure*

To describe the duration of exposure, three durations of exposure will be calculated.

- Duration of study treatment exposure will be defined in weeks as:
(The date of last visit attended – treatment cycle 1 injection date + 1) / 7.
- Duration of treatment cycle will be defined in days as:
For subjects who are retreated at the end of the cycle, the duration of treatment cycle is calculated as (date of retreatment) - (treatment injection date).
For subjects who are not retreated at the end of the cycle, the duration of treatment cycle is calculated as (last attended visit date of the treatment cycle) – (treatment injection date) + 1.
- Duration of Active Treatment exposure will be defined in weeks as:
(The date of last visit attended – first Dysport injection date + 1) / 7.

The following summary tables will be provided:

- Description of study treatment exposure by DB treatment group + overall subjects on the safety population for DB period and overall subjects for the whole active treatment periods.
Study treatment exposure will be described both as a quantitative and qualitative variable.

- Description of duration of treatment cycle, for each treatment cycle, dose received of each treatment cycle and overall subjects from the safety population.
- Description of duration of treatment cycle, by dose received at the cycle and all doses combined on the active treatment population.
Active Treatment exposure will be described both as a quantitative and qualitative variable for each period of exposure.
- A summary table with the total number of subjects who received 1, 2 or 3 active treatment cycles and the total number of subjects who received at least 1, 2 or 3 active treatment cycles, all doses combined on Active treatment population and by DB treatment group + overall subjects.

To describe the doses received, the following summary tables will be provided:

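### SAP 3.2 drops the protocol's double-blind/open-label split of withdrawals, and the exposure formula in SAP 3.9.1 conflicts with the double-blind label of the table that uses it

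*SAP*

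**What the plan says.** **Disposition.** SAP 3.2 lists a summary of subjects screened, randomised and treated, and then "completed, withdrawn and reason for withdrawal by DB treatment group". No period is named. Protocol 11.4.2 says that "the numbers of subjects who discontinued and completed at each of the study periods (double-blind treatment period and open-label period) will be tabulated". Protocol 5.2.4 defines completion by the end-of-study visit: "Subjects who attend the EOS Visit will be considered to have completed the study". SAP section 5 lists four changes from the protocol: the centre-effect description, the intermediate and primary analyses, the COVID-19 start date, and the per-protocol population. The disposition table is not among them.

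**Design.** SAP 1.2 describes a double-blind cycle "followed by an open-label (OL) treatment period (treatment cycles 2 to 4; all subjects receive Dysport". Protocol 3.7.3 allows retreatment from Week 12. In Stage 1 the open-label dose may differ from the subject's first dose (Protocol 3.7.2.1).

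**Exposure.** SAP 3.9.1 defines the duration of study treatment exposure, in weeks, as "The date of last visit attended – treatment cycle 1 injection date + 1) / 7". The table that uses it is specified as "Description of study treatment exposure by DB treatment group + overall subjects on the safety population for DB period and overall subjects", the second part being for the whole of the active treatment periods. The same section defines two other measures: a duration for each treatment cycle, which stops at retreatment, and an active exposure, "The date of last visit attended – first Dysport injection date + 1) / 7".

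**The concern.** Stage 1 asks whether increasing doses are safe, and withdrawals by arm with their reasons are a basic tolerability output. Once placebo subjects can cross to open-label Dysport, a withdrawal status that runs to the end of the study no longer describes the arm it is printed under. A placebo subject who leaves after an open-label injection appears as a placebo withdrawal. A Dysport subject who leaves after retreatment at another dose appears under her first dose. The protocol's period split would keep open-label withdrawals out of the double-blind comparison, and the SAP omits it without saying so.

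The exposure text raises a related but separate problem. A programmer given a double-blind table and a whole-study formula has to choose between them, and the two choices can give very different numbers.

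**Working it through.** The plan states no figure to reproduce here. The check is a comparison of definitions plus simple arithmetic.

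**1. Does SAP 3.2 cover the whole study?**
- Completion means attending the end-of-study visit (Protocol 5.2.4). For a retreated subject that visit falls after open-label treatment, so withdrawal, its counterpart, also spans the open-label cycles.
- SAP 3.1 keeps double-blind tables apart from repeat-treatment tables, but it assigns the table type for each endpoint through SAP 3.8 and 3.9. Disposition is in 3.2.
- Where the SAP wants both periods it says so. SAP 3.6 asks for concomitant-therapy tables for the double-blind period by arm and, in addition, for the active treatment period by cycle. SAP 3.2 has no such wording.

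So 3.2, followed as written, gives one pooled table.

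**2. Size for withdrawals.** Each cohort plans 2 placebo subjects (Protocol 3.1.1), and the final analysis covers cohorts 1 to 6 (SAP 1.3.5).
- Planned placebo subjects: 6 × 2 = 12. Planned Dysport subjects: 5 × 8 + 6 = 46. Total 58.
- One open-label withdrawal counted under placebo: 1/12 = 8.3 percentage points. Two: 2/12 = 16.7. Three: 3/12 = 25.0.

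The documents give no withdrawal counts, so no corrected table can be computed.

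**3. Size for exposure if the formula is used uncut.** Take a cycle 1 injection on Day 1, retreatment on Day 85 (Week 12) and a last visit on Day 337 (Week 48).
- Study treatment exposure formula: (337 − 1 + 1)/7 = 48.1 weeks.
- Double-blind time, by the SAP's cycle-duration rule for retreated subjects: (85 − 1)/7 = 12.0 weeks (12.1 if the extra day is counted).
- With a last visit on Day 253 (Week 36), the formula gives (253 − 1 + 1)/7 = 36.1 weeks.

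Open-label share = (total weeks − double-blind weeks) / total weeks:

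| First retreatment | Last visit | Open-label share |
|---|---|---|
| Week 12 | Week 48 | 36/48 = 75% |
| Week 12 | Week 36 | 24/36 = 67% |
| Week 12 | Week 24 | 12/24 = 50% |
| Week 36 | Week 48 | 12/48 = 25% |
| Never | Any | 0% |

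These timings are assumptions within the protocol's limits. The Week 24 row reflects one open-label cycle followed by the 12-week follow-up after early termination (SAP 1.3.5). If the double-blind label governs, the share is 0% throughout. The formula is the same for placebo and Dysport subjects, so uncut use would lengthen every arm that has retreated subjects.

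**4. What is not touched.**
- SAP 3.9.2 assigns each adverse event to the dose received before onset. It repeats the overall summary, including events leading to drug withdrawal, by dose at each active cycle.
- The Stage 1 primary endpoint ends at Cycle 1 Week 6 (Protocol 3.2.1), before any retreatment.
- SAP 3.9.1 also tabulates cycle duration by cycle and dose received on the safety population, which includes placebo. For retreated subjects, the cycle 1 figure already stops at the open-label injection.

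**The case against.** The best defence is that the gap is one of omission. SAP 3.2 never says that its table covers the whole study, SAP 3.1 introduces the double-blind group labels for the analysis of the double-blind period, and withdrawn subjects are also listed individually. Protocol section 11 lets the SAP modify the protocol's plans and demands formal reporting only for major changes to the primary endpoint or its analysis. The analysis is descriptive and small.

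This limits the consequence but does not supply the missing split. No planned table gives completions and withdrawals by period. Adverse events leading to study discontinuation are only listed, and other reasons for withdrawal appear only in the pooled table and the subject listing.

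On exposure the defence is stronger. A reader might infer that the SAP deliberately counts exposure under each arm for the whole study. The text does not support that: the by-arm table is labelled for the double-blind period, and whole-period exposure is described for overall subjects. It is also on the safety population, analysed as treated, so it is not strictly by randomised arm. What stands is that the label and the only available formula disagree.

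**Conclusion.** The disposition point holds: SAP 3.2 omits a split that Protocol 11.4.2 requires, and SAP section 5 does not record the change. Each placebo subject who withdraws after open-label Dysport would add 8.3 percentage points to the placebo column. That figure assumes the planned 12 placebo subjects; the number analysed may differ, because cohorts could take an extra subject and subjects could be replaced.

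The exposure point holds only as a conflict between formula and label. If the formula is used uncut, open-label time makes up 0% to 75% of a subject's reported exposure. About 48 weeks against 12 is the extreme case, not a typical one.

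Two stronger conclusions are tempting and fail. One is that harm from open-label Dysport moves into the placebo column across the safety results. It does not: adverse events follow the dose received before onset, and the primary endpoint closes before any crossover. The other is that both problems make Dysport look closer to placebo. For exposure no direction is shown, because the Dysport arms are lengthened by the same formula and retreatment timing by arm is not given. The planned adverse event tables are also counts and percentages of subjects, not exposure-adjusted rates.

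**What to change.** In SAP 3.2, tabulate completed, withdrawn and reason for withdrawal separately for the double-blind period, by double-blind treatment group, and for the open-label period. Presenting the open-label part by dose last received is preferable, although this goes beyond Protocol 11.4.2, which asks only for the split by period. If the single table is kept on purpose, record the change in SAP section 5.

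In SAP 3.9.1, define exposure for the double-blind table as ending at the earlier of the first open-label injection and the last visit attended. Keep the whole-study duration for the overall summary.

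The cost is SAP wording and one extra table. Injection dates and doses are already needed for the planned exposure outputs.
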